6.2 Asthma Status Questionnaires

6.2.1 Asthma Clinician Global Impression of Change

The CGI-C instrument is used to evaluate the overall response to treatment. The Investigator (clinician) will be asked to rate the degree to which the overall asthma status may have changed when compared to baseline (Day -1). It is recommended that the same clinician completes the CGI-C at all applicable visits for an individual subject.

Before making the assessment, the clinician will need to access and review the results from all relevant assessments, including pulmonary function tests performed before the visit. The assessment uses a 7-point rating scale: 1=Very Much Improved; 2=Much Improved; 3=Minimally Improved; 4=No Change; 5=Minimally Worse; 6=Much Worse; and 7=Very Much Worse.

Assessment of CGI-C will be conducted as detailed in Table 5 through Table 9 in Section 3.3.

6.2.2 Asthma Control Questionnaire

The Subject ACQ has 7 questions: the top scoring 5 symptoms, FEV₁% predicted, and daily rescue bronchodilator use. Subjects will be asked to recall how their asthma has been during the previous week and to respond to the symptom and bronchodilator use questions on a 7-point scale (0=no impairment; 6=maximum impairment). The Investigator will also score the FEV₁% predicted on a 7-point scale (0=no impairment; 6=maximum impairment). If the ACQ is completed on a visit where FEV₁% predicted is not measured, this question will be answered using the FEV₁% predicted from the first reading taken on the following morning.

The questions are equally weighted and the ACQ score is the mean of the questions and, consequently, ranges from 0 (totally controlled) to 6 (severely uncontrolled). The scale has been validated for use in both the clinical setting and in clinical studies.

The ACQ has strong measurement properties and has been fully validated for use in both clinical practice and clinical studies (Juniper, Bousquet et al. 2006). For clinical practice, clinical studies and epidemiological studies, the ACQ has strong discriminative and evaluative properties which means that it can detect small differences between subjects with different levels of asthma control and it is very sensitive to within-subject change in asthma control over time.

The ACQ can identify the adequacy of asthma control in individual subjects. In general, subjects with a score below 1.0 will have adequately controlled asthma and above 1.0 their asthma will not be well controlled. However, there is a very grey area between 0.75 and 1.25 where subjects are on the borderline of adequate control. On the 7-point scale of the ACQ, a change or difference in score of 0.5 is the smallest that can be considered clinically important.

Assessment of ACQ-7 will be conducted as detailed in Table 4 through Table 9 in Section 3.3.

6.3 Pulmonary Function Tests (Spirometry)

Spirometry will be conducted both to ensure no worsening of asthma during the study and as an exploratory PD endpoint. The spirometric exploratory analyses will be addressed in the Statistical Analysis Plan (SAP).

The site will be provided with a spirometry system with customized, study specific software. The volume accuracy of the spirometer across different flow ranges is to be checked with appropriate documentation via a printed calibration check report, prior to the conduct of spirometry on each test day. See Appendix 2 for spirometry performance criteria.

All study staff responsible for performing spirometry testing will receive training on the provide spirometry system and study specific software. All spirometry technicians are required to demonstrate proficiency in the use of the equipment and the ability to perform technically acceptable and repeatable spirometry sessions prior to performing testing on study subjects (see Appendix 2).

After completion of subject spirometry testing, the study staff will electronically transmit the spirometric measurements for centralized quality assurance review. Feedback on the quality of the spirometry data will be provided to the site and to the Sponsor or designee for central data management.

Spirometry on Screening Visits 1 and 2 will be conducted at 60 minutes and 30 minutes prior to bronchodilator administration and at 30 minutes post-bronchodilator (after 4 puffs of salbutamol).

At Visit 4 (Day 1) and at subsequent dosing visits, spirometry will be conducted approximately 60 minutes and 30 minutes prior to dosing.

At non-dosing visits where spirometry is conducted, 2 assessments will be conducted 30 minutes apart; assessments should be conducted at approximately the same time as on dosing days. No post-bronchodilator spirometry will be performed after Visit 2.

Subjects must withhold all asthma medications, including short-acting bronchodilators, for at least 6 hours before coming into the clinic on all scheduled spirometry visits. Subjects who inadvertently take asthma medication within 6 hours of the start of study procedures must have their clinic visit delayed (but not exceed study drug dosing by 10 AM) or rescheduled within the specified visit window.

Spirometry will be conducted as detailed in Table 4 through Table 9 in Section 3.3.

6.4 Future Analysis of Additional Cytokines

Additional blood samples will be collected as detailed in the Schedule of Events (Table 5 through Table 8 in Section 3.3) and the plasma stored for future analysis of asthma biomarkers not included in this study that would enhance the interpretation of the data generated. Examples of such biomarkers include cytokines (e.g., macrophage inhibitory proteins and IL-1 β) and proteins (e.g., periostin) involved in inflammation, fibrosis, and/or re-modelling. No genetic testing will be performed on these samples.

6.5 Blood Sampling Volume per Subject

The total blood sampling volume for individual subjects in this study will not exceed 800 mL during the course of the study (32 weeks). The actual collection times of blood sampling may change, but the total blood volume collected will not increase. Additional blood samples may be taken for safety assessments at times specified by the Sponsor, provided the total volume taken during the study does not exceed 550 mL during any period of 90 consecutive days.

7 STUDY TREATMENT

7.1 Product Description

UPB-101 injection █ mg/mL is a sterile, colourless to pale yellow, clear to slightly opalescent liquid solution supplied in a single-use vial with a coated rubber stopper and an aluminium cap. The description of UPB-101 and placebo are presented in Table 11.

Table 11 Product Descriptions

Product Description			
Product Name & Potency	Dosing Strength	Dosage Form/ Fill Count	Administration
UPB-101 █ mg/mL	█ mg	█ solution for injection	Delivered as █ mL of the formulated solution per SC injection (containing █ mg UPB-101)
UPB-101 █ mg/mL	█ mg	█ solution for injection	Delivered as █ mL of the formulated solution per SC injection (containing █ mg UPB-101)
Placebo	█ mg matching Placebo	As supplied by site	Delivered as █ mL of normal saline per SC injection.
Placebo	█ mg matching Placebo	As supplied by site	Delivered as █ mL of normal saline per SC injection.

SC=subcutaneous.

7.2 Treatment Administration

UPB-101 or matching placebo will be administered SC at the sites. All study drug dosing should be complete by 12 noon.

A description of the dosing regimens for the study is presented in Table 11 and described in further detail in Section 7.2.1.

Criteria for study drug discontinuation are provided in Section 4.9.1.

7.2.1 Dosing Instructions

Each vial is filled with an overfill sufficient to deliver █ mL of the formulated solution (containing █ mg UPB-101) or placebo.

Site personnel will administer █ mL of formulated solution SC to deliver █ mg of UPB-101, █ mL to deliver █ mg, or placebo per SC injection.

Table 12 Description of SC Dosing Regimens

Description of SC Dosing Regimens in Part A			
Cohort	Treatment Arm and Dosage	Number of Injections to Achieve Dose	Frequency x Number of Doses
Cohort 1	UPB-101 █ mg	█	█
	Placebo		
Cohort 2	UPB-101 █ mg	█	█
	Placebo		
Cohort 3	UPB-101 █ mg	█	█
	Placebo		
Description of SC Dosing Regimens in Part B (Adaptive Design)			
Cohort 4 (optional)	UPB-101 █ mg	█	█
	Placebo		
Cohort 5 (optional)	UPB-101	• █ █ █ █	█
	Placebo		

█; SC=subcutaneous.

In exceptional cases where a subject cannot tolerate multiple SC injections, use of an infusion pump may be considered at the discretion of the Investigator. Administration of the entire dose of study drug via an infusion pump should not exceed 4 hours.

7.2.2 Cohorts with █ Dosing Intervals

In cohorts with █ dosing intervals, the study drug will be administered on Days █ for an █-week Dosing Period. Dosing will begin at █ mg (Cohort 1). Once all 8 subjects have been enrolled in Cohort 1, Cohort 2 (█ mg) will enrol the next 8 eligible subjects.

Prior to the administration of the third dose to subjects enrolled in Cohort 1, the SRC will meet as per Section 5.8. The same process will be repeated prior to the third dosing in Cohort 2.

7.2.3 Cohorts with █ Dosing Intervals

In cohorts with █ dosing intervals, study drug will be administered on Days █ for an █-week Dosing Period.

[figure not shown]
7.2.4 Cohorts with █ Dosing Intervals

In cohorts with █ dosing intervals, study drug will be administered on Days █ for a █-week Dosing Period, except for Cohort 4 where study drug will be administered on Day 1 ONLY. None of the cohorts with █ dosing are dependent upon the SRC recommendations.

7.2.5 Rotation of Injection Sites

Study drug may be administered in any extremity or in the abdominal wall. It is advised that the sites of injection be rotated, and the subject receive study drug injections in different anatomical sites at each administration. One suggested scheme of the injection site rotation is shown in Figure 3. For ease or tracking injection sites, suggested study drug administration locations for one study visit are: one injection in right upper arm, one injection in right abdomen, and one injection in right anterior thigh.

Figure 3 Rotation of Injection Sites

7.3 Preparation/Handling/Storage/Accountability

7.3.1 Acquisition and Accountability

The study drug will be packaged to support enrolment of the study. Qualified study personnel will have access to an IXRS to allocate subjects, to assign drug to subjects and to manage the distribution of clinical supplies. The study drug will be packaged according to a component schedule generated by the Sponsor. Each person accessing the IXRS must be assigned an individual unique personal identification number (PIN). They must use only their assigned PIN to access the system and they must not share their assigned PIN with anyone.

Under no circumstances will the Investigators allow the study drug to be used other than as directed by this protocol.

The study drug must be received by a designated person at the study site, handled and stored safely and properly, and kept in a secure location to which only the Investigator and designated assistants have access. Storage conditions for the study drug should be observed, monitored, and documented. Study drug is to be dispensed only in accordance with this protocol. The Investigator or designee is responsible for keeping accurate records of the study received, the amount dispensed, and the amount remaining at the conclusion of the study. Study drug should be handled in accordance with Good Pharmacy Practices (i.e., gloves should always be worn by study personnel if directly handling any investigational medicinal drug). The Sponsor's blinded Medical Monitor should be contacted with any questions concerning investigational products where special or protective handling is indicated. At the end of the study, study drug should be accounted for and destroyed under local handling procedures and permission from the Sponsor.

Sites should discuss with the Sponsor representative for appropriate documentation that needs to be completed for drug accountability and destruction.

The Investigator or designated assistant should not open individual study drug until all pre-dose assessments have been completed and the subject has been approved by the Investigator to be randomized and enrolled into the study. Any deviation from this must be discussed with the Sponsor's blinded Medical Monitor.

All product complaints must be reported to the Sponsor. The Sponsor will contact the site to evaluate the nature of the complaint and determine what further action is needed, if applicable.

7.3.2 Primary Packaging and Labelling Information

Investigational materials will be packaged by the Sponsor.

Labels will be printed with black ink and may include the following text:

Lot # (Packaging Lot Trace ID) Kit # Expiration date Subject # Investigator Space for subject # Contents Visit # Product identifiers (name and strength)	Storage conditions Protocol # Country regulatory requirements Sponsor name, address, and telephone number Route of administration Directions for use Caution statement (to be used by qualified Investigators only)
--	---

ID=identification; #=number

Each vial will be labelled with a single label to enable blinding of the subjects and all site personnel (except for the designated unblinded dispensing pharmacist).

7.3.3 Secondary Packaging and Labelling Information (Bulk Packaging)

Table 13 Description of Boxes

Drug Supplies	Individual Box Contents
Blinded	████████ per box

Each shipping package will be labelled with a single label printed with black ink and may include the following text:

Protocol #	Route of administration
Kit #	Directions for use
Lot # (Packaging Lot Trace ID)	Caution statement (to be used by qualified Investigators only)
Visit #	Storage conditions
Expiration date	Sponsor name, address, and telephone number
Kit contents	Country regulatory requirements
Product identifiers (name and strength)	

ID=identification; #=number.

7.3.4 Product Storage

UPB-101 should be stored at $-20^{\circ}\text{C} \pm 5^{\circ}\text{C}$. The stability of the UPB-101 has been evaluated at $-20^{\circ}\text{C} \pm 5^{\circ}\text{C}$ (for 36 months) and at $5^{\circ}\text{C} \pm 3^{\circ}\text{C}$ (for 6 months) and the product was found to be stable under these conditions.

7.3.5 Preparation

UPB-101 vials should be placed at room temperature until fully thawed upon visual inspection. Once transferred to a syringe for SC injection, the syringe should be allowed to reach room temperature for approximately 1 hour prior to administration.

7.4 Treatment Assignment

Subjects will be randomized by IXRS in a double-blind fashion to either UPB-101 or matching placebo in a 3:1 ratio. Each subject will be assigned a randomization number by IXRS which will correspond to the treatment and cohort allocation.

7.5 Blinding

Subjects, Investigators, all site personnel (except for the designated unblinded dispensing pharmacist and flow cytometry laboratory personnel) and the blinded CRO team will be blinded to study drug.

The following procedures have been instituted to mitigate the risk of unblinding of the enrolled subjects and blinded site personnel during the study drug administration:

- Qualified study personnel situated in the isolated site pharmacy will prepare the solutions for injection based upon the randomization allocation;

- The study drug and matching placebo will be identical (or nearly identical) in appearance once drawn into the syringe for injection;
- All the prepared syringes will be covered with blinding labels;
- Subjects will be dosed by site personnel trained in blinding techniques and instructed not to discuss the subjects' study drug assignments with blinded site personnel;
- Subjects will be dosed in a cordoned area out of the view of other study subjects (note: site personnel performing dosing may be blinded site personnel, provided all conditions within this section are met).
- The IXRS will be used to control all drug distribution and inventory for this study.

The Sponsor will be unblinded throughout this exploratory study but will not be involved in the treatment or clinical evaluation of the subjects.

All potentially unblinded roles and unblinding parameters within the study will be documented separately and a risk assessment performed to ensure appropriate processes are in place to maintain the blind throughout the blinded period of the study.

Since PK data and PD assessments from individual subjects may be unblinding, such data will be available to the unblinded Sponsor but not to any of the blinded parties. Therefore, until the entire study (i.e., Parts A and B) has been concluded and the database locked, results of eosinophil numbers, FeNO, total IgE, CRP, cytokines, and TSLP will be accessible only to unblinded parties. Summary analyses of the overall PK data will be reported to the SRC (Section 5.8.2). These reports will not contain any unblinded individual PK results. In addition, summary data that might bias blinded personnel will also be inaccessible to blinded parties.

A blinded Medical Monitor will be assigned to support site communications regarding specific subjects and adverse events, assignment of Sponsor causalities and other activities that will be described in the medical monitoring plan.

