6.1.4 Flow Cytometry – pSTAT and Receptor Occupancy

Phosphorylated signal transducer and activator of transcription and receptor occupancy will be assayed via flow cytometry. Blood samples obtained from subjects will be analysed fresh or frozen. The decision to assay the frozen samples will be based on the results from the fresh samples. Analysis of blood samples (whether fresh or frozen) for pSTAT may be discontinued, based on assay status.

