9.4.9 Exploratory Analyses

Analysis of all exploratory PD endpoints (biomarkers, flow cytometry assays, CGI-C, ACQ-7, and FEV_1) will be fully described in the SAP.

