#### ***6.2. Randomisation and Blinding***

Subjects will be randomized by IXRS in a double-blind fashion to either UPB-101 or matching placebo in a 3:1 ratio. Each subject will be assigned a randomization number by IXRS which will correspond to the treatment and cohort allocation. Subjects, Investigators, all site personnel (except for the designated unblinded dispensing pharmacist and flow cytometry laboratory personnel) and the tranScrip team will be blinded to the subjects' allocations.

The following procedures have been instituted to mitigate the risk of unbinding of the enrolled subjects and blinded site personnel during the study drug administration:

Qualified study personnel situated in the isolated site pharmacy will prepare the solutions for injection based upon the randomization allocation;

The study drug and matching placebo will be identical (or nearly identical) in appearance once drawn into the syringe for injection;

All the prepared syringes will be covered with blinding labels;

Subjects will be dosed by site personnel trained in blinding techniques and instructed not to discuss the subjects' study drug assignments with blinded site personnel;

Subjects will be dosed in a cordoned area out of the view of the blinded site personnel and of other study subjects.

The Sponsor will be unblinded throughout this exploratory study but will not be involved directly in the treatment or clinical evaluation of the subjects.

All potentially unblinded roles and unblinding parameters within the study will be documented separately and a risk assessment performed to ensure appropriate processes are in place to maintain the blind throughout the blinded period of the study.

Since PK data and some PD assessments from individual subjects may be unblinding, such data will be available to the unblinded Sponsor but not to any of the blinded parties. Therefore, until the entire study (i.e., Parts A and B) has been concluded and the database locked, results of eosinophil numbers, FeNO, total IgE, CRP, cytokines, and TSLP will be accessible only to unblinded parties.

Summary analyses of the overall PK data will be reported to the SRC. These reports will not contain any unblinded individual PK results.

A blinded Medical Monitor will be assigned to support site communications regarding specific subjects and adverse events, assignment of Sponsor causalities and other activities that will be described in the medical monitoring plan.

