### **10.11.1. Biomarkers**

The biomarkers collected in the study include cytokines (IL-5, IFN λ, IP-10, TSLP, eotaxin-3, TARC and lab parameters (Eosinophils, Total IgE and C-reactive protein). Receptor occupancy evaluated by flow cytometry, considered as a biomarker for target engagement, is also included.

All biomarkers, with the exception of the flow cytometry biomarker, will be summarized by visit as absolute values, change from baseline and percentage change from baseline, by treatment group. Any scheduled pre-baseline data will also be summarized by visit and treatment group.

Flow cytometry based evaluation of receptor occupancy (free receptors) will be calculated as the difference between the signal intensity (measured as % of TSLPR+ CD14+ cells) of the test sample and an aliquot of the same sample incubated ex vivo with saturating levels of UPB-101 prior to adding the detection antibody. The receptor occupancy will then be summarized at each visit, along with the percentage of free receptors, where;

% free receptors at any timepoint (t) = (difference between signal intensity at timepoint (t) / difference between signal intensity at baseline )\* 100.

For negative % Free Receptors, set the value to 0. For % Free Receptors greater than 100%, set the value to 100%.

For all biomarkers the baseline will be the last non-missing result prior to first dose.

Any data that is below the limit of quantification will be replaced with zero before summarising but will be listed as '<BLQ'.

A mean plot of the biomarker results over time will be displayed, where the plots will display the mean at each visit +/- the standard error, with a line per treatment group.

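### Flow cytometry staff are exempt from blinding to allocation with no reason given and no reading safeguard, so arm-dependent reading of the exploratory receptor-occupancy marker is not excluded

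*Protocol*

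**What the plan says.** Protocol 7.5 (Blinding) lists who is blinded to study drug: subjects, investigators, and "all site personnel (except for the designated unblinded dispensing pharmacist and flow cytometry laboratory personnel) and the blinded CRO team will be blinded". SAP 6.2 has the same exemption, "all site personnel (except for the designated unblinded dispensing pharmacist and flow cytometry laboratory personnel) and the tranScrip team will be blinded", and its sentence ends by naming the subjects' allocation as the thing withheld.

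For the pharmacy, Protocol 7.5 describes a task that needs the allocation: qualified staff there "will prepare the solutions for injection based upon the randomization allocation". No such task is described for the flow cytometry laboratory.

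SAP 10.11.1 gives the marker its role: "Receptor occupancy evaluated by flow cytometry, considered as a biomarker for target engagement, is also included". The signal is "measured as % of TSLPR+ CD14+ cells) of the test sample and an aliquot of the same sample" that has first been saturated with UPB-101. Free receptors are then expressed as a percentage of the subject's own baseline difference, with negative values set to 0 and values above 100% set to 100%.

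On stored samples, Protocol 6.1.4 says: "The decision to assay the frozen samples will be based on the results from the fresh samples". It does not say who decides. Protocol 9.4.9 places the flow assays among the exploratory PD endpoints, and SAP 10.1.4 plans no formal statistical analysis.

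Protocol 7.5 also says that individual PD data may be unblinding and go to no blinded party. It promises a separate record of unblinded roles with a risk assessment. It then names the results restricted to unblinded parties: eosinophils, FeNO, IgE, CRP, TSLP and the cytokines. Flow cytometry is not named, although the general sentence on PD data covers it.

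**The concern.** A laboratory that turns a sample into a number does not ordinarily need to know the arm. Flow cytometry involves choices that can move the number: where the positivity gate is placed, whether a run is repeated, which run is accepted. If the allocation is available to the person making those choices, borderline samples can be read lower on active and higher on placebo. A bias of this kind does not shrink as subjects are added. With 6 active subjects per cohort and descriptive summaries only, it would pass straight into the reported means.

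The stake is the evidence of target engagement. Under Protocol 3.1.1, PD results, together with safety and PK, inform the Part B regimens. Under Protocol 1.6 they help choose the Phase 2 dose and frequency. SAP 13.2 puts both flow cytometry tables into the administrative interim as well as the final analysis.

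**Working it through.** The documents contain no figure to reproduce. The check is a reading of the text plus a bound.

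**1. Is arm an input?** From SAP 10.11.1, with T the test-aliquot signal and S the saturated-aliquot signal:

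- D(t) = difference between T(t) and S(t)
- % free(t) = 100 × D(t) / D(0), truncated to the range 0 to 100

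The inputs are two aliquots of one sample and the subject's baseline. Arm does not enter.

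**2. Is the reading protected?** Neither document specifies coded samples, a gating rule, a repeat-run rule or a blinded re-read for this assay.

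**3. What could a reader move?** A gate shift g that acts equally on both aliquots cancels: (T + g) − (S + g) = T − S. Only a net shift in D matters.

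**4. Bound on a post-baseline shift.** Assume, since the documents give nothing, that D(t) is moved by 10% or 20% of D(0). Then % free moves by 10 or 20 points before truncation:

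| True % free | Read, 10% shift | Read, 20% shift |
|---|---|---|
| 5 | 0 to 15 | 0 to 25 |
| 50 | 40 to 60 | 30 to 70 |
| 100 | 90 to 100 | 80 to 100 |

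Take the direction that favours the drug (active read lower, placebo read higher):

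- Active 5, placebo 100: the true contrast is 95. At most it reads 100 − 0 = 100, an inflation of 5 points under either shift.
- Active 50 (for example in washout), placebo 100: the true contrast is 50. It reads 100 − 40 = 60 or 100 − 30 = 70, an inflation of 10 or 20 points, all from the active arm because placebo is at the cap.

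**5. Baseline.** Flow cytometry is first scheduled on Day 1 (Protocol Table 5; there is none in the screening schedule). Protocol 3.1.2 puts randomisation after the Day 1 baseline assessments, so no allocation exists when the sample is drawn. It can be read with knowledge of arm only if it is read later. Protocol 6.1.4 allows fresh or frozen analysis, so this is possible. Overreading D(0) by 10% or 20% on active turns a true 50 into 50 / 1.1 = 45.5 or 50 / 1.2 = 41.7. Because D(0) is the denominator, it rescales every later value of that subject. Underreading D(0) on placebo gives 100 / 0.9 = 111.1 or 100 / 0.8 = 125, both capped at 100.

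**The case against.** **The exemption may only record a fact.** Receptor occupancy shows whether UPB-101 is on its receptor, so whoever reads it can largely infer the arm. A reader might infer from the text that the laboratory holds the randomisation list. The documents do not say so, and it is an equally good reading that the exemption acknowledges unblinding by the data. This stands, and the point is therefore about what is permitted, not what happens. It does not dispose of the point. A baseline result says nothing about arm, and intermediate values are less self-revealing, whereas an allocation list identifies the arm for every sample.

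**Deleting the exemption would create a contradiction.** Protocol 7.5 lets individual PD data reach no blinded party. If the laboratory were simply declared blinded, it would be barred from the results it produces. This stands and shapes the fix.

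**The effect is easily overstated.** A reader might take a gate shift of 1 to 5 points on a baseline difference of 30 to 60, obtain 100 × 1/60 = 1.7 to 100 × 5/30 = 16.7 points, and double it for the contrast between arms. The documents give neither quantity. The calculation treats the whole gate shift as net, ignoring cancellation between aliquots, and doubling needs both arms to be mid-range, whereas untreated placebo subjects should sit near the cap. Extending the target-engagement claim to pSTAT is not supported either: SAP 10.11.1 makes it for receptor occupancy only, and Protocol 6.1.4 allows pSTAT analysis to be discontinued.

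**Procedures may exist elsewhere.** Laboratory instructions or the separate record of unblinded roles may already cover coding and gating. That is possible. However, the risk assessment in Protocol 7.5 is stated to serve keeping the blind. Nothing says that it governs how staff already outside the blind read samples.

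**Conclusion.** The point holds in a limited form. Both documents exempt the flow cytometry laboratory from blinding to allocation without a reason. The SAP formula has no use for the arm, and no coded-sample or pre-set gating requirement is stated. Arm-dependent reading of the exploratory target-engagement marker is therefore permitted, chiefly at intermediate occupancy and for any baseline sample read after randomisation.

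The size cannot be derived from the documents. Under the assumed net shift of 10% or 20% of the baseline difference, it is 10 or 20 points at 50% free receptors and at most 5 points on a contrast of 5% against 100%. The within-sample saturated control and the truncation both limit it. That the laboratory does not need the allocation is an inference from the formula, not a statement in either document.

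The primary safety endpoints do not use this readout, and no test depends on it. The change is worth making because it protects a marker that feeds dose decisions at almost no cost. It is not a threat to the trial's main conclusions.

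**What to change.** In Protocol 7.5 and SAP 6.2, replace the blanket exemption with wording to this effect:

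- Flow cytometry personnel are not given the allocation. They are listed as potentially unblinded by their own results.
- Samples reach the laboratory coded by subject and visit only.
- Gating and repeat-run rules are fixed on control samples before any study sample is read.
- The choice of frozen samples to assay is sent to the laboratory as sample IDs, without allocation.
- Flow cytometry is added to the named list of results open only to unblinded parties, with an explicit allowance for the laboratory that generates them.

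The cost is a small amount of wording in the two documents and in the laboratory instructions. If there is a reason why the laboratory must hold the allocation, Protocol 7.5 should state it.
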